#### **14.3.2.2 Analysis of the other efficacy variables**

Other efficacy variables will be summarized by treatment and visit and will generally be summarized based on imputed data (NRI and multiple imputation [MI] for binary and continuous variables, respectively, unless otherwise stated in the SAP). In some cases, variables may also be summarized based on observed case data (ie, subjects with missing data or who have prematurely discontinued IMP are treated as missing). There may be cases where the multiple imputation model fails to converge. In such situations, the last observation carried forward (LOCF) approach will instead be used to impute the missing data. If LOCF is used instead of multiple imputation for this reason, this will be clearly specified in the corresponding table summary. Should there be no missing data for a study variable, then only observed case data will be presented. Note that for LOCF imputation, any missing data or data collected following

discontinuation of IMP will be imputed with the most recent previous value. See [Section 14.7](#) for further details.

Time to PASI75/90/100 response will be estimated and presented using the Kaplan-Meier product-limit method based on the RS by initially randomized treatment groups (Bimekizumab vs secukinumab). This could make the interpretation of the data challenging given that there are two different bimekizumab dosing regimens starting at Week 16, but it is anticipated that most responses will be observed by Week 16 when all bimekizumab subjects are on the same regimen. Time to a given response will be defined as the length in days from the first dose of IMP until the first date when the response is achieved. Subjects who discontinue IMP prior to achieving a response will be censored at the date of IMP discontinuation. Subjects who reach the Week 48 Visit without achieving the given PASI response will be censored at the date of the Week 48 Visit. The median time to response, including the 2-sided 95% CI, will be calculated for each treatment. Between group differences (bimekizumab vs secukinumab) will be analyzed with the log-rank statistic.

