For other continuous efficacy variables, MI will be used to impute missing data when possible. If the imputation model cannot converge, LOCF will be used. The MI procedure will be similar to sensitivity analysis #1 described above with the following differences: (1) the imputation model will use the change from Baseline (instead of actual) values by visit and no dichotomization will be necessary; (2) instead of using the stratified CMH test, the imputed data sets will be combined and simple means and standard errors will be calculated using Rubin's rules (via SAS PROC MIANALYZE). For calculation of other descriptive statistics such as the median, minimum and maximum, Rubin's rules do not apply. Multiple imputation estimates will be computed by simply averaging the estimates from the multiple repetitions of the imputation algorithm.

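### For the other continuous efficacy variables, LOCF as the fallback when multiple imputation fails lets convergence, not design, decide which mean a table reports

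*Protocol*

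**What the plan says.** Section 14.7: "For other continuous efficacy variables, MI will be used to impute missing data when possible". The next sentence gives the fallback: "If the imputation model cannot converge, LOCF will be used". The MI resembles the first sensitivity analysis for the primary variable, which the same section describes as assuming missing at random and as targeting the outcome under full adherence. The output is limited: "simple means and standard errors will be calculated using" Rubin's rules.

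Section 14.3.2.2 says "There may be cases where the multiple imputation model fails to converge" and then "In such situations, the last observation carried forward (LOCF) approach will instead be used to impute the missing data". It requires disclosure: "If LOCF is used instead of multiple imputation for this reason, this will be clearly specified in the corresponding table summary". It also defines what LOCF replaces: "for LOCF imputation, any missing data or data collected following" the "discontinuation of IMP will be imputed with the most recent previous value".

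Two other places bear on the point. Section 6.5, criterion 8b, directs that from Week 28 subjects on treatment for at least 12 weeks whose IGA stays at 3 or more for at least 4 weeks stop IMP. Section 14.3.1.1 handles non-convergence of the logistic model by removing prior biologic exposure and then region, and of the centre-interaction model by pooling centres.

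**The concern.** The fallback is a fixed rule, so the objection is to its content and not to an omission. Two neighbouring tables could report different quantities, one the adherence mean under missing at random and the other a mean of last values, for no reason beyond a fitting failure. A label tells the reader that this happened but does not make the two comparable.

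LOCF also holds each leaver at an earlier score. If the group was still improving, the late mean looks worse than it would have been under adherence. If poor responders leave more often, their last poor score is carried to the end with no allowance for regression toward the group mean. Criterion 8b builds that kind of leaving into the trial. At stake is how faithful the descriptive means are for variables such as percent change in PASI, DLQI and mNAPSI.

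**Working it through.** The protocol gives no figure for LOCF bias, for non-convergence, or for dropout, SD or correlation in these variables. Its only remark on dropout, in Section 14.3.1, is that few are expected to discontinue before Week 16. There is therefore no stated figure to reproduce, and every input below except the group sizes 117 and 350 is an assumption.

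**Inputs**
- Five visits, normal scores with SD 1, correlation 0.7 between adjacent visits (0.7 to the power of the lag).
- Mean change at visits 1 to 5: −1.5 × (0.30, 0.55, 0.80, 0.95, 1.00) SD. Lower is better.
- Monotone dropout d of 5%, 10% or 20% by visit 5.
- Groups of 20, 40, 117 and 350. Section 14.9 gives 350 per arm, and the 1:2 re-randomization gives 350/3 ≈ 117 on Q4W.
- Target: the mean at visit 5 if all had adhered.

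**Scenario (a): scores improving, leaving unrelated to score.** The dropout probability per interval is h = 1 − (1 − d)^(1/4). The share last seen at visit t is h(1 − h)^(t−1), for t = 1 to 4. The LOCF bias is the sum of share × (mean at t − mean at 5), where the gaps are 1.050, 0.675, 0.300 and 0.075 SD.
- d = 5%: h = 0.0127; 0.0134 + 0.0085 + 0.0037 + 0.0009 = 0.0265 SD.
- d = 10%: h = 0.0260; 0.0273 + 0.0171 + 0.0074 + 0.0018 = 0.0536 SD.
- d = 20%: h = 0.0543; 0.0570 + 0.0346 + 0.0146 + 0.0034 = 0.1096 SD.

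**Scenario (b):** as (a), but the log-odds of leaving rise by 0.7 per SD worse last score. Realised dropout was somewhat above nominal: about 6%, 12% and 23%.

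**Scenario (c):** nearly flat scores (one tenth of the change in (a)), leaving unrelated to score. The formula gives one tenth of (a): 0.003, 0.005 and 0.011 SD.

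LOCF bias toward less improvement, from 2000 simulated groups per setting (range over the four group sizes, in SD):

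| Dropout | (a) by hand | (a) simulated | (b) simulated | (c) simulated |
|---|---|---|---|---|
| 5% | 0.027 | 0.023–0.030 | 0.056–0.057 | 0.003–0.010 |
| 10% | 0.054 | 0.050–0.061 | 0.108–0.119 | 0.007–0.009 |
| 20% | 0.110 | 0.109–0.110 | 0.205–0.213 | 0.005–0.018 |

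The excess of (b) over (a) is about 0.03, 0.06 and 0.10 SD. It reflects selective leaving together with the slightly higher realised dropout. Flat scores with selective leaving were not simulated, so the near-nil result in (c) applies only when leaving is unrelated to score.

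**Comparison.** MI that imputes each visit from the preceding visit only (10 imputations, Rubin's rules, 250 groups per setting) had bias of at most 0.013 SD in every setting. The data were generated in a form that suits this model, so the comparison is favourable to it.

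**The case against.** The strongest case on the other side is that the consequence is small and the remedy could sit in the SAP. The rule touches only descriptive summaries. The secondary variables are all binary and, like the primary, use nonresponder imputation. Use of LOCF must be labelled. Section 14.7 leaves MI details to the SAP, and trying simpler models before declaring that MI cannot converge would fit the present wording. The limited consequence stands in full. The deferral does not cancel a stated endpoint: as written, failure of the imputation model leads to LOCF.

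Four stronger readings are tempting, and the documents do not support them.
- *Intervals lose coverage in small subsets.* Sections 14.2 and 14.7 plan no confidence interval for these variables. If one were shown, the loss would come from bias and grow with group size: in (b) at 20% dropout, coverage is 88.8% at n = 20, 79.1% at 40, 47.9% at 117 and 6.1% at 350.
- *Non-convergence is likely in the nail, PsA or Q4W groups.* The protocol says only that it may happen and names no variable or subset.
- *The LOCF standard error is too small.* In the simulation it was 0.97 to 1.03 of the true sampling SD.
- *Replacing scores collected after discontinuation is itself an error.* The observed-case rule in Section 14.3.2.2 also treats subjects who discontinued IMP as missing, and the adherence target points the same way. Little is affected: Section 8.5 gives leavers one premature end-of-treatment assessment, and the follow-up visits in Sections 8.6 and 8.7 have no efficacy scores.

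**Conclusion.** The point holds as a minor one. The stated fallback changes the quantity reported according to convergence, and it biases the mean when scores are moving or poor responders leave. Under the assumptions above, the bias is about 0.02 to 0.06 SD at 5% dropout, 0.05 to 0.12 SD at 10% and 0.11 to 0.21 SD at 20%, against at most 0.013 SD for a reduced imputation model. With nearly flat scores and unrelated dropout it is at most 0.02 SD.

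These sizes depend on assumed dropout, correlation and trajectory. Criterion 8b supports the direction of scenario (b) from Week 28 but not its exact strength. Whether the fallback will be used at all is unknown. No primary, secondary or multiplicity-controlled conclusion is at risk.

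**What to change.** In Sections 14.3.2.2 and 14.7, replace the LOCF fallback with a fixed order of simpler imputation models, taken in turn until one converges:
1. Drop auxiliary covariates.
2. Impute each visit from the preceding visit only.
3. Add a ridge prior.

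If all fail, show observed cases with the number observed. This last step can also be biased under selective leaving, but it carries no values forward and shows how much is missing. Keep the requirement to state in the table which method was used.

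Keep scores collected after IMP discontinuation out of these analyses, in line with the observed-case rule and the adherence target. The sentence that now says this for LOCF should be reworded to apply to the imputation models, not simply deleted.

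The order follows the step-down that Section 14.3.1.1 already uses for the logistic model. The cost is wording in two sections, a little programming and one or two extra model-fitting steps to pre-specify. No new data are needed.

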## 14.8 Planned interim analysis

An interim analysis is planned at Week 48 and Week 144, details of which will be documented in the SAP. Additional interim analyses may be performed (details of which will be documented in the SAP). Corresponding interim Clinical Study Reports (CSRs) may be written. A final analysis and updated final CSR will be prepared once all data through the OLE2 Period and SFU2 Visit have been collected.

## 14.9 Determination of sample size

A total of 700 subjects will be randomly assigned in a 1:1 ratio at Baseline to one of the following treatment groups:

- Bimekizumab 320mg (350 subjects)
- Secukinumab (350 subjects)

The primary efficacy analysis is based on the comparison of bimekizumab to secukinumab for the primary efficacy variable of PASI100 response at Week 16. The assumed responder rates for PASI100 at Week 16 are 60% and 44% for bimekizumab and secukinumab, respectively. The assumed responder rate for bimekizumab is based on the Phase 2b PS0010 data. The assumptions related to the responder rates for secukinumab are based on those observed in the CLEAR study (Thaçi et al, 2015). The power to show statistical superiority of bimekizumab relative to secukinumab under these assumptions is 98% for the primary endpoint. The power for the non-inferiority comparison (with 10% non-inferiority margin) under these assumptions is >99%.

## 15 ETHICS AND REGULATORY REQUIREMENTS

### 15.1 Informed consent

Subject's informed consent must be obtained and documented in accordance with local regulations, ICH-GCP requirements, and the ethical principles that have their origin in the principles of the Declaration of Helsinki.

Prior to obtaining informed consent, information should be given in a language and at a level of complexity understandable to the subject in both oral and written form by the Investigator (or designee). Each subject will have the opportunity to discuss the study and its alternatives with the Investigator.

Prior to participation in the study, the ICF should be signed and personally dated by the subject and by the person who conducted the informed consent discussion (Investigator or designee). The subject must receive a copy of the signed and dated ICF. As part of the consent process, each subject must consent to direct access to his/her medical records for study-related monitoring, auditing, IRB/IEC review, and regulatory inspection.

All subjects enrolling in the OLE Period will sign a new ICF. Similarly, all subjects enrolling in the OLE2 Period will sign a new ICF.

If the ICF is amended during the study, the Investigator (or the sponsor, if applicable) must follow all applicable regulatory requirements pertaining to the approval of the amended ICF by the IRB/IEC and use of the amended form.

All studies conducted at centers in the United States must include the use of a Health Insurance Portability and Accountability Act Authorization form.

The subject may withdraw his/her consent to participate in the study at any time. A subject is considered as enrolled in the study when he/she has signed the ICF. An eCRF must not be started, nor may any study specific procedure be performed for a given subject, without having obtained his/her written consent to participate in the study.

## **15.2 Subject identification cards**

Upon signing the Informed Consent and Assent form (as applicable), the subject will be provided with a subject identification card in the language of the subject. The Investigator will fill in the subject identifying information and medical emergency contact information. The Investigator will instruct the subject to keep the card with him/her at all times.

## **15.3 Institutional Review Boards and Independent Ethics Committees**

The study will be conducted under the auspices of an IRB/IEC, as defined in local regulations, ICH-GCP, and in accordance with the ethical principles that have their origin in the Declaration of Helsinki.

The Investigator/UCB will ensure that an appropriately constituted IRB/IEC that complies with the requirements of the current ICH-GCP version or applicable country-specific regulations will be responsible for the initial and continuing review and approval of the clinical study. Prior to initiation of the study, the Investigator/UCB will forward copies of the protocol, ICF, IB, Investigator's curriculum vitae (if applicable), advertisement (if applicable), and all other subject-related documents to be used for the study to the IRB/IEC for its review and approval.

Before initiating a study, the Investigator will have written and dated full approval from the responsible IRB/IEC for the protocol.

The Investigator will also promptly report to the IRB/IEC all changes in the study, all unanticipated problems involving risks to human subjects or others, and any protocol deviations, to eliminate immediate hazards to subjects.

The Investigator will not make any changes in the study or study conduct without IRB/IEC approval, except where necessary to eliminate apparent immediate hazards to the subjects. For minor changes to a previously approved protocol during the period covered by the original approval, it may be possible for the Investigator to obtain an expedited review by the IRB/IEC as allowed.

As part of the IRB/IEC requirements for continuing review of approved studies, the Investigator will be responsible for submitting periodic progress reports to the IRB/IEC (based on IRB/IEC requirements), at intervals appropriate to the degree of subject risk involved, but no less than once per year. The Investigator should provide a final report to the IRB/IEC following study completion.

UCB (or its representative) will communicate safety information to the appropriate regulatory authorities and all active Investigators in accordance with applicable regulatory requirements. The appropriate IRB/IEC will also be informed by the Investigator or the sponsor, as specified by the applicable regulatory requirements in each concerned country. Where applicable,

Investigators are to provide the sponsor (or its representative) with evidence of such IRB/IEC notification.

#### **15.4 Subject privacy**

UCB staff (or designee) will affirm and uphold the subject's confidentiality. Throughout this study, all data forwarded to UCB (or designee) will be identified only by the subject number assigned at Screening.

The Investigator agrees that representatives of UCB, its designee, representatives of the relevant IRB/IEC, or representatives of regulatory authorities will be allowed to review that portion of the subject's primary medical records that directly concerns this study (including, but not limited to, laboratory test result reports, ECG reports, admission/discharge summaries for hospital admissions occurring during a subject's study participation, and autopsy reports for deaths occurring during the study).

#### **15.5 Protocol amendments**

Protocol changes may affect the legal and ethical status of the study and may also affect the statistical evaluations of sample size and the likelihood of the study fulfilling its primary objective.

Significant changes to the protocol will only be made as an amendment to the protocol and must be approved by UCB, the IRB/IEC, and the regulatory authorities (if required), prior to being implemented.

### **16 FINANCE, INSURANCE, AND PUBLICATION**

Insurance coverage will be handled according to local requirements.

Finance, insurance, and publication rights are addressed in the Investigator and/or CRO agreements, as applicable.

## 18 APPENDICES

### 18.1 Protocol Amendment 1

#### Rationale for the amendment

The primary rationale for this amendment was to incorporate a re-randomization at Week 16 for subjects in the bimekizumab 320mg treatment arm. At Week 16 subjects in the bimekizumab 320mg treatment arm will be re-randomized 1:2 to receive bimekizumab 320mg Q4W or bimekizumab 320mg Q8W.

The following additional changes were also made:

- Add the number of subjects included in the summary of the completed study UP0042
- Clarify the scalp IGA and pp-IGA efficacy response criteria
- Move the PHQ-9 variable from an other safety variable to an other efficacy variable
- Added percent of subjects achieving mNAPSI75, mNAPSI90, and mNAPSI100 for subjects with nail PSO at Baseline as an other efficacy variable
- Clarify that all study assessments should be performed prior to administration of IMP
- Clarify the study visit windows
- Clarify that the PGADA should be performed on all subjects at Baseline
- Define mental healthcare professional
- Clarify the assessment and management of TB wording
- Clarify the drug accountability wording
- Revise the systemic retinoid washout period
- Clarify that the same assessor should evaluate the subject at each assessment
- Remove the requirement for a rheumatologist evaluation for subjects with a PASE  $\geq 47$
- Clarify the IMP restart/rechallenge requirements in case of PDILI
- Add the definition of the Enrolled Set and Maintenance Set
- Revise the statistical analysis based on the addition of re-randomization at Week 16

Minor spelling, editorial, and formatting changes were also made, and the List of Abbreviations was updated.

#### Modifications and changes

##### Change #1

##### Section 1 Summary

During the Treatment Period, eligible subjects will be randomized 1:1 to receive one of the following blinded IMP regimens:

- Bimekizumab 320mg administered subcutaneously (sc) every 4 weeks (Q4W)

- Secukinumab 300mg administered sc at Baseline and Weeks 1, 2, 3, and 4 followed by dosing Q4W

Subjects receiving bimekizumab 320mg will receive placebo sc on Weeks 1, 2, and 3 in order to maintain the blind.

Approximately 350 subjects will be randomized to bimekizumab 320mg and approximately 350 subjects will be randomized to secukinumab. Investigational medicinal product will be administered at Baseline, Weeks 1, 2, 3, and 4 and then Q4W thereafter, until Week 44 (Treatment Period). All doses will be administered in the clinic.

#### **Has been changed to:**

During the **first 16 weeks of the** Treatment Period, eligible subjects will be randomized 1:1 to receive one of the following blinded IMP regimens:

- Bimekizumab 320mg administered subcutaneously (sc) every 4 weeks (Q4W)
- Secukinumab 300mg administered sc at Baseline and Weeks 1, 2, 3, and 4 followed by dosing Q4W

Subjects receiving bimekizumab 320mg will receive placebo sc on Weeks 1, 2, and 3 in order to maintain the blind.

Approximately 350 subjects will be randomized to bimekizumab 320mg and approximately 350 subjects will be randomized to secukinumab. Investigational medicinal product will be administered at Baseline, Weeks 1, 2, 3, and 4 and then Q4W thereafter, until Week 44 (Treatment Period). All doses will be administered in the clinic.

**At Week 16 subjects in the bimekizumab 320mg treatment arm will be re-randomized 1:2 to receive bimekizumab 320mg Q4W or bimekizumab 320mg every 8 weeks (Q8W). To maintain the blind after re-randomization, subjects in the bimekizumab 320mg Q8W treatment arm will receive placebo at Weeks 20, 28, 36, and 44. Subjects in the secukinumab arm will continue to receive secukinumab 300mg Q4W.**

#### **Change #2**

##### **Section 2.2.1.1 Completed studies**

Five clinical studies of bimekizumab have been completed: UP0008 in 39 subjects with mild to moderate plaque PSO, RA0124 in 30 healthy volunteers, PA0007 in 53 subjects with PsA, UP0031 in 12 healthy volunteers, and UP0042 in healthy volunteers.

#### **Has been changed to:**

Five clinical studies of bimekizumab have been completed: UP0008 in 39 subjects with mild to moderate plaque PSO, RA0124 in 30 healthy volunteers, PA0007 in 53 subjects with PsA, UP0031 in 12 healthy volunteers, and UP0042 in **48** healthy volunteers.

#### **Change #3**

##### **Section 2.2.1.2 Ongoing studies**

Seven additional studies of bimekizumab in the treatment of PSO are ongoing.

- PS0008 is a Phase 3, multicenter, randomized, double-blind, parallel-group, active-comparator-controlled study to evaluate the efficacy and safety of bimekizumab in adult subjects with moderate to severe chronic plaque PSO.
- PS0009 is a Phase 3 randomized, double-blind, placebo- and active comparator-controlled study to evaluate the efficacy and safety of bimekizumab administered sc to adult subjects with moderate to severe plaque PSO.
- PS0010 is a Phase 2b, double-blind, placebo-controlled, dose ranging study to evaluate the safety, efficacy, PK, and pharmacodynamics (PD) of bimekizumab in adult subjects with moderate to severe chronic plaque PSO.
- PS0011 is a long-term extension study for subjects who completed PS0010 to assess the long-term safety, tolerability, and efficacy of bimekizumab.
- PS0013 is a Phase 3, multicenter, randomized withdrawal, double-blind, placebo-controlled study to evaluate the efficacy and safety of bimekizumab in adult subjects with moderate to severe chronic plaque PSO.
- PS0016 is a Phase 2a, subject-blind, investigator-blind study to evaluate the time course of PD response, safety, and PK of bimekizumab in adult subjects with moderate to severe chronic plaque PSO.
- PS0018 is a long-term extension study for eligible subjects from PS0016 to assess the safety, tolerability, and efficacy of bimekizumab.
- PS0014 is a Phase 3, multicenter, open-label study to assess the long-term safety, tolerability, and efficacy of bimekizumab in adult subjects with moderate to severe chronic plaque psoriasis.

